10.3.4.2 Efficacy - Daily Insulin Use

Hypothesis:

Multiple doses of REMD-477 will significantly decrease daily insulin use versus placebo treatment at Week 12.

The daily insulin use will be derived as the average daily insulin over a collection period ranging from either 3 or 7 days. For the Lead-In Period (Part A – 14 to 28 days; Part B – 7 to 14 days), the average daily insulin use will be derived from a period of 14 days. For Days 1, 8, 15, and 22, the average daily insulin use will be derived from the individual insulin values over the next 7 days. For Days 50, 78, 106 and 134, the average daily insulin use will be derived from the individual insulin values over the next 3 days. Baseline assessment is the derived average daily insulin use during the Lead-In (Part A – 14 to 28 days; Part B – 7 to 14 days) period. The measurements will be summarized separately for Parts A and B by treatment group and timepoint along with changes and percentage changes from baseline. Figures of mean average daily insulin use, changes and percentage changes from baseline will be presented separately for Parts A and B by treatment.

The changes from baseline and percentage change from baseline measurements will be statistical analyzed separately for Parts A and B. The statistical analysis for the changes from baseline measurements will be used to test the primary hypothesis, while the statistical analysis for the percentage changes from baseline measurements will be used as a sensitivity analysis. A sequential stepwise hypothesis and a Hochberg testing procedure will be utilized to allow for multiple testing while preserving the overall significance level of the trial.

For Parts A and B separately a repeated measures ANCOVA will be used to compare the changes and percentage changes from baseline in daily insulin use between treatment groups for each timepoint. Dependent variables will be treatment, day, and the treatment by day interaction. The baseline variable will be used as a covariate. Covariates may be added to the above model depending on the results from the comparison of baseline characteristics as detailed in section [10.3.4.1](#)

Subject will be used as a random effect. The least squares (LS) mean for each treatment will be presented for each timepoint. Also, the difference between treatments, the 95% confidence interval (CI) of the differences, and p-value associated with the null-hypothesis of no difference will be reported for each timepoint where applicable based on the sequential testing methods as described below.

Step 1: The first step of the sequential testing will consist of a test for the effect of REMD-477. The Hochberg procedure will be used to assess the statistical significance of two tests: one for the superiority of 70 mg REMD-477 compared to placebo, the other for the superiority of 35 mg REMD-477 compared placebo. If the larger of the two p-values is less than the significance level (ie, 0.05), then both tests are considered to have reached statistical significance. Otherwise, if the smaller of the two p-values is less than half of the significance level (ie 0.025), then the corresponding test is considered to have reached statistical significance.

Step 2: If at least one of the two doses of REMD-477 is found to be superior to placebo, then the two doses of REMD-477 will be compared using the same significance level as that used to claim significance of either dose of REMD-477.

10.3.4.3 Fasting Glucose, MMTT and Arginine Challenge Test – Part A only

The following section applies to Part A only.

The fasting glucose concentrations, concentrations following the MMTT and Arginine Challenge Test (ACT), will be summarized by treatment group and timepoint, along with changes from baseline. The percentage changes from baseline for fasting glucose concentrations will also be summarized by treatment group and timepoint. Figures of mean profiles, changes and percentage changes from baseline will be presented by treatment. The baseline fasting glucose is the last value measured prior to the first study drug dosing. The MMTT baseline is the average value from the -10 minute and -1 minute timepoints for each MMTT. The ACT baseline is the 0 minute timepoint, which is equivalent to the 120 minute timepoint of the MMTT.

The difference in glucose concentration following MMTT will be derived as the glucose concentration at the 120 minute timepoint at MMTT, minus the MMTT baseline glucose concentration. This metric will be summarized by treatment group and study day, along with changes from baseline, where baseline is the defined as the metric obtained at the Lead-in (OBV) period for those subjects enrolled prior to amendment # 1 of the protocol or the baseline visit for those thereafter.

Concentrations of glucose, c-peptide, glucagon, insulin, GLP-1 (active and total) will be used to derive the respective AUC (unadjusted and adjusted by test baseline) from the MMTT and ACT for each study day.

AUC will be calculated using the linear trapezoidal method. To calculate AUC adjusted for baseline, the baseline concentration value will be subtracted from all post-test concentrations. Any negative values after baseline adjustment will be set to zero.

AUC calculations, where possible, will be carried out using actual post-dose times recorded in the raw data. If actual times are missing, nominal times may be used with sponsor approval. The baseline for AUC of each parameter is the value derived from the concentrations obtained at the Lead-In (OBV) period for those subjects enrolled prior to Amendment # 1 of the protocol or the baseline visit for those thereafter.

The change from baseline measurements for fasting glucose, the change from baseline difference in glucose concentration following MMTT, and the change from baseline of the derived AUC for glucose, C-peptide, glucagon, insulin and GLP-1 (active and total), unadjusted and adjusted by test baseline, will be statistically analyzed. The percentage change from baseline for the derived AUC, unadjusted and adjusted by test baseline for C-peptide, will also be statistically analyzed. A repeated measures ANCOVA will be used to compare the each of these parameter between treatment groups for each timepoint. Dependent variables will be treatment, day, and the treatment by day interaction. The baseline variable will be used as a covariate. Covariates may be added to the above model depending on the results from the comparison of baseline characteristics as detailed in section 10.3.4.1

Subject will be used as a random effect. The LS mean for each treatment will be presented for each timepoint. Also, the difference from placebo, the 95% CI of the difference from placebo, and p-value associated with the null-hypothesis of no difference will be reported for each timepoint.

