After the Lead-in Period (which includes the completion of the two week CGM period), eligible subjects will be admitted to the CRU around 4:00 pm for a single overnight stay on one of the following study days: Day -8, -7, -6, -5, -4, -3, or -2 relative to the subject's scheduled dosing day (Day 1). The OBV must be performed within 8 days (check-in to occur between Day -8 to Day -2) prior to administration of study drug.

At the time of admission, data from the DexCom CGM device, the subject's diary capturing insulin use, and the seven-point glucose measurements will be obtained and reviewed. CGM results from the study DexCom device will be downloaded and typical measures of glycemic control (mean glucose, standard deviation, time in range) will be recorded. CGM results will be unblinded throughout the study.

Additionally, the following baseline assessments will be completed: medical history, physical exam, body weight, urine pregnancy test, urine drug and alcohol test, 12-lead ECG, and vital signs, per the Schedule of Assessments. Safety and PD labs, including serum chemistry, hematology, urinalysis, HbA1c, insulin, C-peptide, glucagon, serum ketones, free fatty acids (FFA), and GLP-1 will be collected. Fasting plasma glucose samples will be collected on the following morning, prior to the administration of the MMTT and Arginine Challenge Tests. During the 8 hour overnight fast, plasma glucose via YSI will be measured hourly, and subjects will be allowed to receive juice by mouth, in case of hypoglycemia.

For subjects on insulin pumps: Subjects will be admitted to the CRU at approximately 1600 (4:00 pm). A peripheral IV will be placed at this time. They will be given a standard dinner at 1800 (6:00 pm) for which they can bolus as they normally would via their insulin pump for that particular meal. At approximately 1900 (7:00 pm), the subject's insulin pump will be disconnected and suspended and IV insulin infusion will begin. Blood glucose control will be maintained per [Appendix C](#) to maintain euglycemia in the 90-120 mg/dl range with start rates

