At Week 13 (1 week after receiving Dose 12) and Week 24 (End of Study Visit), a subset of subjects in Part A enrolled prior to Protocol Amendment #1, will be admitted to the CRU to complete an MMTT and arginine challenge test, after an overnight fast of at least 8 hours in a similar manner as done at the Overnight Baseline Visit. During the 8 hour overnight fast, plasma glucose via YSI will be measured hourly, and subjects will be allowed to receive juice by mouth, in case of hypoglycemia. During both challenge tests, C-peptide, glucagon, insulin, GLP-1, and glucose concentrations will be measured. Stimulated C-peptide will be measured with the ultra-sensitive C-peptide kit from Mercodia.

For ongoing or newly enrolled subjects participating in Part A at the time of Protocol Amendment #1, overnight admission to the CRU on Week 13 and Week 24 will not occur. For these visits, subjects will return to the CRU to complete all the study procedures outlined in the Schedule of Assessments table – however, all assessments for that visit will be performed on a single day (i.e., the Week 13 Visit will be performed on Day 85, and the Week 24 Visit will be performed on Day 162).

For subjects enrolled in Part A:

- **Please Note:** For ongoing or newly enrolled subjects in Part A at the time of Protocol Amendment #1, the MMTT will only be administered at the Baseline and Week 13 visits, after the subject completes an 8 hour overnight fast at home (the MMTT is no longer required at Week 24). No Arginine Challenge Tests or YSI assessments will be performed for these subjects.

For subjects enrolled in Part B:

- **Please Note:** Neither the MMTT assessment nor Arginine Challenge Test assessment will be conducted.

Subjects will also be given an insulin usage diary at the beginning of weeks 16 and 20.

For these weeks, assessments of the daily insulin requirements will be obtained by taking the average total daily insulin dose (short-acting, long-acting, and infusional as applicable) over a period of three consecutive days within that respective week.

Subjects who early terminate from the study during the 12-week treatment period will be monitored for 12 weeks after the last injection of study drug (REMD-477 or placebo).

Throughout the Study: Day 1 through End of Study

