On the mornings of the MMTT days (Overnight Baseline, Day 85, and Day 162), a subset of subjects enrolled in Part A prior to the Protocol Amendment #1 will be awakened by 7:00 am after an overnight fast of at least 8 hours. During the 8 hour overnight fast, plasma glucose via YSI will be measured hourly, and subjects will be allowed to receive juice by mouth, in the case of hypoglycemia. Prior to and during the MMTT, the subjects will be at rest (sitting or lying down), with quiet activities such as reading or TV watching.

At Time 0, subjects will begin a standard meal for the MMTT. As they will be on an IV infusion of insulin, the rate of insulin infusion should be continued at the time 0 rate for the duration of the MMTT and arginine stimulation procedure. No bolus insulin be given prior to the MMTT.

For all other subjects enrolled or are ongoing at the time of the Protocol Amendment #1, the overnight admissions to the CRU at Baseline, Week 13 and Week 24 will not occur. These subjects will return to the CRU in the morning to complete the MMTT at Baseline and Week 13 visits, after an 8 hour overnight fasting at home. Fasting plasma glucose samples will also be collected, prior to the administration of the MMTT. For all subjects, fasting blood glucose should be 80-180 mg/dl. During the overnight fasting at home, subject can drink juice or take glucose tabs if hypoglycemic. No rapid acting insulin should be taken within 4 hours prior of the MMTT.

For subjects on insulin pumps: The insulin pump will continue until the completion of the MMTT.

For subjects on insulin injections with basal insulin given at night: Subjects can take their last dose of long acting insulin in the evening prior to the Baseline Visit.

For subjects on insulin injections with basal insulin given in the morning: Subjects will take their normal AM dose of basal insulin in the morning a day prior to the Baseline Visit, as well as on the morning of the MMTT.

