15. APPENDICES

Appendix A. Schedule of Assessments – Part A

Study Period (or Dose #)	Screen	Lead-In		Dose 1		Dose 2	Dose 3	Dose 4	Dose 5	Dose 6	Dose 7	Dose 8
Study Week	≤ 42 days		Baseline Visit	1		2	3	4	5	6	7	8
Study Day		2 to 4 Weeks	Day -8/-7 to Day -2/-1	Pre-dose	1	8 ± 1	15 ± 1	22 ± 1	29 ± 1	36 ± 1	43 ± 1	50 ± 1
Informed consent	X											
Medical History ^a	X		X									
Physical examination	X		X						X			
Height (Screening only) & Body weight	X	X	X						X			
Urine pregnancy test (women); FSH ^g	X		X						X			
Urine drug/alcohol test	X		X						X			
12-lead ECG ^b	X		X						X			
Vitals (BP, RR, HR, T) ^c	X	X	X	X		X	X	X	X	X	X	X
Chemistry, Hematology, Lipid Panel, and Urinalysis	X		X			X	X		X		X	
Fasting (≥ 8-hr) plasma glucose ^e			X	X		X	X	X	X	X	X	X
Serum Ketones & Free Fatty Acids			X	X		X	X	X	X	X	X	X
Study Drug SC Administration					X	X	X	X	X	X	X	X
Seven-point blood glucose profile ^d		X						X				X
Unblinded Continuous Glucose Monitoring (CGM) ^h		X										
Ketone finger-stick ^j					X	X	X	X	X	X	X	X
Daily insulin usage dairy ⁱ		X			X	X	X	X	X			X
Hourly plasma glucose via YSI ^e			X ¹									
Mixed Meal Tolerance Test (MMTT) ^e			X									
Arginine Challenge Test ^e			X ¹									
HbA1c	X		X									
Insulin, C-peptide, GLP-1, and Glucagon ^{e,f}			X						X			
Serum PK sample collection ^f				X		X			X			
Anti-REMD-477 Ab sample collection ^f				X								
Exploratory biomarker collection				X								
QOL Questionnaires ^k			X									
Overnight Admission ^l			X									
Con-Med monitoring	X											
Adverse event monitoring												

Footnote Key:

- a. Medical history includes significant past medical events (e.g. prior hospitalizations or surgeries), a review of diabetes history and glycemic control, and any concurrent medical illnesses.
- b. After the Screening Visit, 12-lead ECG to be performed in triplicate, approximately 1 min apart. When ECG and blood sample collection occur at the same time, ECGs should be performed before blood samples are drawn.
- c. Vital signs include blood pressure, respiratory rate, heart rate, and oral temperature.
- d. Seven-point blood glucose profile will measure glucose by finger stick over three consecutive days before and 2 hours after each meal, and at bedtime.

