- e. **For a subset of subjects enrolled prior to Protocol Amendment #1:** subjects should fast overnight for 8 hours prior to MMTT. During the overnight fast, plasma glucose via YSI will be measured hourly, and subjects will be allowed to receive juice by mouth, in case of hypoglycemia. For the Overnight Baseline Visit (OBV), Day 85 visit and Day 162 Visit, fasting plasma glucose samples will be collected on the morning following admission, prior to the administration of the MMTT and Arginine Challenge Tests. MMTT must be completed prior to the Arginine Challenge Test.

For ongoing or newly enrolled subjects at the time of Protocol Amendment #1: overnight admission to the CRU at Baseline, Week 13, and Week 24 will not occur. For these visits, subjects will still return to the CRU to complete all the study procedures outlined here in the Schedule of Assessments table – however, all assessments for that visit will be performed on a single day (*Baseline Visit: Day -8 to Day -1; Week 13 Visit: performed on Day 85; and Week 24 Visit: performed on Day 162*).

- **Note:** For ongoing or newly enrolled subjects at the time of Protocol Amendment #1, the MMTT will only be administered at the Baseline and Week 13 visits, after the subject completes an 8 hour overnight fast at home (the MMTT is no longer required at Week 24). No Arginine Challenge Tests or YSI assessments will be performed for these subjects.
- f. Sample should be collected pre-dose on all dosing days.
- g. FSH required at screening for post-menopausal women.
- h. Unblinded CGM will be performed for two weeks during the Lead-in Period (completed prior to the OBV), and throughout the study Dosing and Follow-up Periods from Dose 1 through the End of Study Visit. For on-going or newly enrolled subjects in Part A at the time of Protocol Amendment #2, CGM data will be collected throughout the study from Dose 1 through the Day 85/Week 13 Visit, and CGM devices will be “unblinded”. CGM data will be downloaded at the clinical research unit during scheduled site visits, as indicated in the Schedule of Assessments.

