Appendix A. Schedule of Assessments – Part B

Study Period (or Dose #)	Screen	Lead-In	Dose 1		Dose 2	Dose 3	Dose 4	Dose 5	Dose 6	Dose 7	Dose 8
Study Week	≤ 42 days		1		2	3	4	5	6	7	8
Study Day		1 to 2 Weeks	Baseline/ Pre-dose	1	8 ± 1	15 ± 1	22 ± 1	29 ± 1	36 ± 1	43 ± 1	50 ± 1
Informed consent	X										
Medical History ^a	X		X								
Physical examination	X		X					X			
Height (Screening only) & Body weight	X	X	X					X			
Urine pregnancy test (women); FSH ^f	X		X					X			
Urine drug/alcohol test	X		X					X			
12-lead ECG ^b	X		X					X			
Vitals (BP, RR, HR, T) ^c	X	X	X		X	X	X	X	X	X	X
Chemistry, Hematology, Lipid Panel, and Urinalysis ^e	X		X		X	X		X		X	
Fasting (≥ 8-hr) plasma glucose ^e			X		X	X	X	X	X	X	X
Serum Ketones & Free Fatty Acids ^e			X		X	X	X	X	X	X	X
Study Drug SC Administration				X	X	X	X	X	X	X	X
Seven-point blood glucose profile ^d		X					X				X
Blinded Continuous Glucose Monitoring (CGM) ^g		X		X			X				X
Daily insulin usage dairy ^h		X	X	X	X	X					X
HbA1c	X		X						X		
Insulin, C-peptide, GLP-1, and Glucagon ^e			X					X			
Serum PK sample collection ^e			X		X			X			
Anti-REMD-477 Ab sample collection ^e			X								
Exploratory biomarker collection ^e			X								
Liver Injury Biomarkers ^e			X					X			
Liver MRI/ FibroScan ^j			X								
QOL Questionnaires ⁱ			X								
Con-Med monitoring	X		◀	▶							
Adverse event monitoring			◀	▶							

Footnote Key:

- a. Medical history includes significant past medical events (e.g. prior hospitalizations or surgeries), a review of diabetes history and glycemic control, and any concurrent medical illnesses.
- b. After the Screening Visit, 12-lead ECG to be performed in triplicate, approximately 1 min apart. When ECG and blood sample collection occur at the same time, ECGs should be performed before blood samples are drawn.
- c. Vital signs include blood pressure, respiratory rate, heart rate, and oral temperature.
- d. Seven-point blood glucose profile will measure glucose by finger stick over three consecutive days before and 2 hours after each meal, and at bedtime.
- e. Sample should be collected pre-dose on all dosing days.
- f. FSH required at screening for post-menopausal women.
- g. Blinded CGM will be performed for one week during the Lead-in Period (completed prior to the Baseline Visit), and for one week after Doses 1, 4, 8 and 12. CGM data will be downloaded at the clinical research unit during scheduled site visits, as indicated in the Schedule of Assessments.

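### Part A fasting glucose at Week 13: subjects admitted overnight are sampled on Day 85 during an IV insulin infusion, their values enter the treatment comparison, and Part B's uninfused samples get no comparison

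*SAP*

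**What the plan says.** The secondary endpoint is change from baseline at Week 13 in fasting glucose, limited to Part A in both the protocol (Section 10) and the SAP (10.3.2). SAP 10.3.4.3 opens with "The following section applies to Part A only" and sets the baseline: "The baseline fasting glucose is the last value measured prior to the first study drug dosing". For the MMTT glucose difference and the AUCs, the same section instead uses the Overnight Baseline Visit (OBV) or Baseline Visit value.

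For the pre-Amendment #1 subset, Week 13 and Week 24 are overnight admissions with testing "after an overnight fast of at least 8 hours in a similar manner as done at the Overnight Baseline Visit". At that visit IV insulin starts at about 7 pm and is adjusted "to maintain euglycemia in the 90-120 mg/dl range". Protocol Section 7 (Mixed Meal Tolerance Test) has these subjects still on the infusion when the meal begins. Footnote e of the Part A schedule says that at the OBV, Day 85 and Day 162 "fasting plasma glucose samples will be collected on the morning following admission", before the MMTT.

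The other Part A subjects attend as outpatients after fasting at home, and the protocol says: "For all subjects, fasting blood glucose should be 80-180 mg/dl". Part B has no OBV, Baseline Visit, MMTT or infusion. Its schedule still carries the row "Fasting (≥ 8-hr) plasma glucose", marked at Day 1 pre-dose, every dosing visit, Day 85 and Day 162.

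**The concern.** A fasting glucose drawn while insulin is being infused to a glucose target measures how well the infusion was run. A drug effect would show as a lower infusion rate, not a lower glucose. The Day 85 treatment-by-day term nevertheless pools these values with ordinary fasting values. The expected result is a difference from placebo that is too small, and a within-arm fall from the uninfused Day 1 baseline that would appear even on placebo. The risk is an understated effect, not a false positive.

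The trial also holds Day 1-to-Day 85 fasting samples from Part B, collected with neither infusion nor MMTT preparation. The SAP plans no treatment comparison for them.

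**Working it through.** **1. Which sample is the baseline.** Part A fasting draws in Appendix A: Baseline Visit 1 + Day 1 pre-dose 1 + Days 8-50 7 + Days 57-78 4 + Day 85 1 + Day 162 1 = 15. Table 7-1 states 15. Without the Day 1 draw the count is 14, so the stated figure needs both pre-dose samples, and the last value before dosing is Day 1. If that sample is missing, the rule falls back to the OBV value, which for this subset is itself on infusion.

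**2. Conditions at each sample.**
- Day 1: morning visit; no infusion and no glucose window stated.
- Days 8-78: routine fasting samples at dosing visits.
- Day 85, admitted subjects: after a night of IV insulin, target 90-120 mg/dL (Appendix C).
- Day 85, other Part A subjects: home fast, 80-180 mg/dL wording.
- Day 85, Part B: home fast, no MMTT.

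**3. A bound from the protocol's own figures.** In the type 2 diabetes study (Protocol Section 2, R477-201), fasting glucose fell 45-52 mg/dL on active doses and up to 10 on placebo. The difference is at least 45 − 10 = 35 to 52 − 10 = 42 mg/dL. The infusion target is 120 − 90 = 30 mg/dL wide. Two arms held in target cannot differ by more than 30.

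**4. Illustration within infused subjects.** Assumptions not in the documents: ordinary fasting mean m = 150-190 mg/dL on placebo, SD s = 40-70, true difference 40, every value inside [a, b]. With α = (a − m)/s and β = (b − m)/s, the mean of a truncated normal is m + s[φ(α) − φ(β)]/[Φ(β) − Φ(α)].

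One case, s = 40, [90, 120]:
- Placebo, m = 150: 150 + 40(0.1295 − 0.3011)/(0.2266 − 0.0668) = 107.0.
- Active, m = 110: 110 + 40(0.3521 − 0.3867)/(0.5987 − 0.3085) = 105.2.
- Visible difference 1.8 mg/dL. Placebo falls 43 mg/dL from Day 1 with no drug effect.

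Over the full range of m and s, the visible difference is 0.6-1.8 mg/dL and the spurious placebo fall is 43-84 mg/dL.

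**5. Effect on the pooled Day 85 difference.** With an infused fraction f, equal across arms in expectation: pooled = (1 − f) × 40 + f × (0.6 to 1.8). The protocol does not give f, so a range is shown.
- f = 10%: 36 + 0.06 to 0.18 = 36.1-36.2
- f = 30%: 28 + 0.18 to 0.54 = 28.2-28.5
- f = 50%: 20 + 0.3 to 0.9 = 20.3-20.9

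**6. The 80-180 wording.** The same formula with every value inside 80-180 gives a visible difference of about 6-17 mg/dL for a true 40. This is an upper bound on the loss: the wording says what the value should be, and no rule says what happens when it is not.

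**The case against.** Several points against a stronger reading stand.

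- A reader might infer that the Part A data before Day 85 go unused. They do not. SAP 10.3.4.3 fits a repeated measures ANCOVA with treatment by day and reports the difference from placebo, CI and p-value at each timepoint, so the Day 78 contrast is already planned.
- A reader might call Day 78 or Part B undistorted. From Day 1 all subjects in both parts are told to titrate basal insulin to a pre-breakfast glucose of 80-120 mg/dL (Protocol Section 7). Some narrowing of the arm contrast is therefore built into every fasting value. Those samples are free of the infusion, not of titration.
- A reader might infer that the Day 1 baseline biases the arm comparison. The mismatch applies to every randomised arm and baseline is a covariate, so it mainly distorts within-arm change. The attenuation comes from the Day 85 conditions.
- The infused group may be small. Subjects ongoing at Amendment #1 had no further overnight admissions, so only those who reached Week 13 before it are affected.
- Truncation at 90-120 is a crude model of an infusion that the investigator may adjust.
- The Part A limit comes from the protocol endpoint, so it is not a SAP slip. Part B glycaemia is also modelled through CGM, seven-point profiles and HbA1c.
- Moving the endpoint to Day 78 would read it after 11 doses rather than 12, and would change a timepoint after a Part A interim that SAP section 12 says has taken place.

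None of this makes an on-infusion value a measure of fasting glucose under study treatment.

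**Conclusion.** The point holds for one defined group: Part A subjects admitted overnight at Week 13, and any Day 162 values from subjects admitted then. Their values reflect the infusion and pull the difference from placebo toward zero. The pooled loss is roughly in proportion to their share of Day 85 values, which is not stated; the figures in step 5 rest on assumed means, SDs, true difference and shares.

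The documents do not support extending this to all of Part A. The 80-180 mg/dL wording carries no enforcement rule and is at most a secondary concern. This is a secondary endpoint outside the Hochberg procedure, so the primary conclusion is untouched. The remedy is inexpensive and improves validity, which is the reason to make it.

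**What to change.** In SAP 10.3.4.3:

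1. Keep Week 13 (Day 85) as the named timepoint.
2. Exclude from the fasting-glucose repeated measures model any value taken after an overnight IV insulin infusion (Day 85, Day 162, and an OBV value that would otherwise serve as baseline). Identify these by overnight admission at that visit. The rule depends on procedure, not on treatment or result. Report how many values it removes in each arm.
3. Give the all-values model as a sensitivity analysis.
4. Name the already planned Day 78 contrast as supportive.
5. Run the same model in Part B, Day 1 baseline to Day 85. Protocol Section 10 lists fasting glucose for repeated measures ANCOVA without limiting that sentence to Part A, but the endpoint is Part A only, so this is an addition.

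Declare items 2 and 5 in SAP section 12, with the date relative to the interim, because SAP section 11 allows sponsor study teams to be unblinded at such analyses.

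Cost: no new samples; fewer Day 85 values in Part A; one extra model in Part B (about 25 subjects per group at most); and a declared departure from the protocol's Part A-only endpoint. Admitted subjects still contribute their Day 8-78 values.
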